9.7 Data Analysis

The following describes the statistical analysis as it is foreseen at the time of planning the trial. Detailed methodology for the summary and statistical analyses of data collected in this study will be documented in a Statistical Analysis Plan (SAP).

9.7.1 Populations for Analysis

The following analysis sets will be defined:

- The Lamzede Safety analysis set (L-SAF) will contain all enrolled patients fulfilling inclusion criteria who have, at some time, received Lamzede treatment. This will include all patients entering the study currently taking Lamzede and all patients not taking Lamzede on entry to the study, but who begin doing so during the study. The latter group (those not taking Lamzede on entry to the study, but who begin doing so during the study) will only be classed as in the L-SAF from the time that they begin taking Lamzede. As is common practice, patients who have taken any amount of Lamzede, even if only one dose, will be included in the safety analyses. With regards to L-SAF definition, a minimum individual follow up of 1 month after last dose taken will be proposed. A consequence of this approach, where patients can be in the L-SAF for very varying amounts of time is that adverse event (and adverse reaction) rates will be presented based on person-years at risk, and not simply based on the total number of patients who are ever in the L-SAF.
- The Lamzede Effectiveness analysis set (L-FAS) will contain patients included in the Lamzede Safety analysis set at the times when they have been taking Lamzede, and for 12 months thereafter excluding patients without any valid measurement and those with major protocol deviations affecting the effectiveness evaluations. The consequence of this is that

Clinical Protocol Number: CLI-LMZYMAA1-12	
Clinical Protocol Version Number: 8.0	Date: 01 February 2019

"baseline" will be clearly defined for each patient – namely the time they started to take Lamzede, not necessarily the time they enter the study. So a patient can be excluded from the L-FAS for some of their time in the study, and then join the L-FAS. In such cases, their "baseline" would be the time when they started.

- The No-Lamzede Safety analysis set (NL-SAF) will include patients only for the time when they are not (and have not within 1 month) been taking Lamzede.
- The No-Lamzede Effectiveness analysis set (NL-FAS) will include patients only for the time when they are not (and have not within the 12 months) been taking Lamzede.

Exact definitions of major Protocol deviations will be discussed by the clinical team case by case during the Data Review Meeting and described in the Data Review Document.

A summary table reporting the reason for exclusion from analysis sets will be presented.

The primary objective of the study (i.e. to assess the long-term effectiveness and safety of treatment with Lamzede) will be based on the Lamzede Safety analysis set (L-SAF) for safety variables and on the Lamzede Effectiveness analysis set (L-FAS) for effectiveness and other variables.

The secondary objectives of the study will be based on the No-Lamzede Safety analysis set (NL-SAF) for safety variables and on the No-Lamzede Effectiveness analysis set (NL-FAS) for effectiveness and other variables.

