Figure 1 Alpha-Mannosidosis Treatment Response Models Treatment Response Model

Chiesi	
Clinical Protocol Number: CLI-LMZYMAA1-12	
Clinical Protocol Version Number: 8.0	Date: 01 February 2019

Source: Provided by Chiesi

Based on the MCID-based Treatment Response Model, the Global Response to Treatment (GRT) of rhLAMAN-05 shows a discernible treatment difference between the two groups, with a clinical response in at least two domains at 12 months observed in 87% of patients treated with velmanase alfa compared to 30% in placebo. Moreover, 13% treated patients but none of the placebo patients reported a clinically-significant response in all three domains (Figure 3).

In the single-arm, integrated analysis from rhLAMAN-10 study, a remarkably similar proportion of 79% of patients showed a significant response in at least two domains at 12 months, 24% in all three. The proportion increases at Last Observation with a clinically meaningful response in at least two domains achieved in 88% patients (100% of paediatric patients and 71% of adult patients) and in at least three domains in 45% patients (53% of paediatric patients and 36% of adult patients) (Figure 2). The proposed domains are aligned with the representation of (a) the clinical burden, (b) the endpoints hierarchy defined with the CHMP, (c) the measurements of the benefit perceived by the patients (health-related QoL).

Figure 2 Global Response to Treatment in rhLAMAN-10 Study Integrated Analysis

Collesi	
Clinical Protocol Number: CLI-LMZYMAA1-12	
Clinical Protocol Version Number: 8.0	Date: 01 February 2019

The most common adverse reactions observed during treatment with Lamzede were weight increase (18%), infusion-related reactions (9%), diarrhoea (12%), headache (9%), arthralgia (9%), increased appetite (6%) and pain in the extremities (6%). A total of two serious adverse reactions (loss of consciousness in one patient and acute renal failure in one patient) considered possibly related to study treatment were observed; both cases recovered without sequelae. For further safety information, refer to the Lamzede SmPC.

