8. RESEARCH QUESTION AND OBJECTIVES

Primary Objective

- To assess the long-term effectiveness and safety of treatment with Lamzede under conditions of routine clinical care.
- In terms of effectiveness, the primary focus of the registry is to estimate the Global Treatment Response rate as percentage of patients qualified as responders by aggregately assessing oligosaccharides in serum (umol/L), (GTR-Pharmacodynamic Domain), 3MSCT (step/min), 6MWT (mt), FVC (% of predicted) (GTR-Functional Domain) and QoL based on CHAQ VAS-Pain and CHAQ- Disability Index (GTR-QoL Domain).
- In terms of safety, the rate of AEs (including ADA, IRRs and Hypersensitivity as identified risks) in the treated patients will be the main research of the study.

Secondary Objectives

- To characterize the alpha-mannosidosis population, including clinical manifestation, progression and natural history.
- In particular, oligosaccharides in serum (umol/L), endurance based on 3MSCT (step/min), 6MWT (m) and 2MWT (m) assessment, respiratory function through FVC (as litre and as percentage of predicted), hearing function with PTA, length and rate of infections (requiring or not antibiotics), rate of psychotic events, immunological status as per serum IgG, IgA and IgM, and QoL assessed by EQ-5D-5L, Zarit Burden Interview, CHAQ, Behavior Checklists (prescholar, scholar, adult and older adult) will be adopted for characterizing the alpha-mannosidosis population
- Rate of incidence of acute renal failure and loss of consciousness (as potential risks under Lamzede treatment), change in vital signs (SBP, DBP), laboratory tests (haematology and chemistry), physical examination and ECG will also be monitored.

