9. RESEARCH METHODS

9.1 Study Design

The Registry is a multi-centre, multi-country, non-interventional, prospective cohort including alpha-mannosidosis patients, despite any treatment they received or are receiving. The Registry will be conducted under conditions of routine clinical practice, without registry-mandatory assessments according to the treating physician and will include all eligible patients who agree to participate.

Within the Registry, a pool of patients with alpha-mannosidosis undergoing Lamzede therapy will be suitable to allow a further data collection revolved to the long-term safety and effectiveness of Lamzede therapy (see Section 9.7.4 for the study endpoints). In this group of patients, Lamzede has to be administered in accordance with the current Lamzede SmPC and in line with usual clinical practice. Patients with alpha-mannosidosis receiving and not receiving Lamzede will be also enrolled. It is expected that the pool of patients not receiving Lamzede will be limited in number and characterized by distinct clinical features and/ or a short follow-up duration. This does not permit the definition of a control group and a direct, formal determined *a-priori* between-group comparison, allowing for a descriptive, explorative between-groups comparison only.

Clinical Protocol Number: CLI-LMZYMAA1-12

Clinical Protocol Version Number: 8.0

If applicable in accordance with routine clinical practice, the following schedule of visits is recommended:

- **Registry Inclusion Visit**, at the time of enrolment into the Registry approximately 7 days prior to the Registry Baseline visit. In order to check eligibility criteria and when the informed consent form could also be signed in case to patient willingness to participate to the study;
- **Registry Baseline Visit**, corresponding for all patients included, to the time in which the observational period will start (Time 0) and when the site can also evaluate to possibly start or continue the treatment with Lamzede according to clinical practice;
- Six-month and Yearly follow-up visits for all patients included in the registry;

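### Section 9.7.1 assigns every secondary objective to the off-Lamzede sets, which contradicts section 8, where those objectives include potential risks of Lamzede and a description of the whole disease population

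*Protocol*

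**What the plan says.** Section 8 of the protocol sets out the secondary objectives in three bullets. The first two ask for a characterisation of the alpha-mannosidosis population, including progression and natural history, and name the measures to be used. Neither is limited to untreated patients. The third begins "Rate of incidence of acute renal failure and loss of consciousness (as potential risks under Lamzede treatment" and adds changes in vital signs, laboratory tests, physical examination and ECG.

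Section 9.7.1 defines four analysis sets and assigns objectives to them. For safety, the primary objective "will be based on the Lamzede Safety analysis set (L-SAF) for safety variables". For the rest it says: "The secondary objectives of the study will be based on the No-Lamzede Safety analysis set (NL-SAF) for safety variables". The sentence then assigns the remaining variables of the secondary objectives to NL-FAS. No Lamzede set is named for any secondary objective.

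NL-SAF "will include patients only for the time when they are not (and have not within 1 month) been taking Lamzede". The definition of NL-FAS has the same form, with a gap of 12 months since Lamzede in place of 1 month. On the size of the untreated group, section 9.1 says: "It is expected that the pool of patients not receiving Lamzede will be limited in number".

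**The concern.** A rate that is meant to monitor a possible harm of a drug needs time on that drug in its denominator and events during that time in its numerator. The set named for this objective excludes both. A SAP that follows 9.7.1 would report a background rate under the heading of a treatment risk. A SAP that does not follow it would depart from the protocol.

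Section 7.2 describes the registry as an additional pharmacovigilance activity under the EU Risk Management Plan and an obligation of an authorisation under exceptional circumstances. Section 7.1 explains where the two risks come from: "A total of two serious adverse reactions (loss of consciousness in one patient and acute renal failure in one patient", both considered possibly related to study treatment. With events this rare, a report must be clear about which exposure its denominator represents.

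The characterisation objective has a milder form of the same problem. It is worded for the whole disease population but assigned to off-Lamzede time, in a pool that section 9.1 expects to be small.

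**Working it through.** No power or precision figure is involved. The check sets the passages side by side.

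| Secondary objective (section 8) | Set assigned (9.7.1) | What that set contains |
|---|---|---|
| Acute renal failure and loss of consciousness as potential risks of Lamzede | NL-SAF | Time off Lamzede and more than 1 month after it |
| Vital signs, laboratory tests, physical examination, ECG | NL-SAF | As above |
| Characterisation of the disease population | NL-FAS | Time off Lamzede and more than 12 months after it |
| Natural history | NL-FAS | As above, with never-treated and post-Lamzede time together |

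**Step 1: the potential risks.** An incidence rate is events divided by person-years at risk. Split a patient's follow-up into time before Lamzede, time on Lamzede, the first month after stopping, and later time off Lamzede. NL-SAF keeps only the first and last parts. On-Lamzede time adds 0 events and 0 person-years, and so does the first month after stopping. The result is a background rate by construction.

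**Step 2: the earlier cases.** Section 7.1 reports one case of each event and 33 patients in the clinical programme. Taking 33 as the denominator, 1/33 = 3.0% for each event, with an exact 95% interval of about 0.1% to 15.8%. The interval shows how little is known. A similar event arising during dosing, or in the first month after it, could not enter NL-SAF.

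**Step 3: is there another route to an on-treatment rate?** Probably yes.
- Section 9.7.5 lists acute renal failure and loss of consciousness among the safety variables and applies the adverse-event proportions and person-time rates to potential risks. It names no analysis set.
- Section 9.7.1 places the safety variables of the primary objective in L-SAF and says that adverse-event rates there use person-years at risk.
- The abstract (section 4) covers potential risks in its paragraph on the safety of Lamzede.
- The primary safety objective in section 8 is the rate of adverse events in treated patients. It names the identified risks as included; the potential risks appear only under the secondary objectives.

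**Step 4: population characterisation.** Section 9.7.3 summarises demographics, genotype, enzyme activity and disease history without restriction to untreated time. Most measures named in the secondary objective are also effectiveness variables (9.7.4) or other variables (9.7.6), which are analysed in L-FAS under the primary objective. Treated patients are therefore described, but under a different objective. None of the four sets is all enrolled patients.

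**Step 5: precision.** The exact interval table in section 9.5 was recomputed at n = 70. The widths are 0.239, 0.234, 0.225, 0.214 and 0.199, as stated. Nothing here affects it.

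**The case against.** The strongest defence is that the sets are meant to be read together: safety variables in L-SAF for the drug, and the same variables in NL-SAF as context. Step 3 supports this. In section 8, moreover, the phrase about Lamzede treatment qualifies the risks rather than the rate. A reader might infer that no on-treatment rate of acute renal failure or loss of consciousness would be produced and that the objective could not be answered at all. The documents do not support that, because the primary objective probably supplies the rate. What remains is that section 9.7.1 gives no such combined reading for the secondary objectives and sends them to the No-Lamzede sets without exception.

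A reader might also infer that treated patients go uncharacterised. Step 4 shows otherwise.

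A third tempting reading is that natural history must rest on never-treated patients alone, because NL-FAS readmits patients 12 months after they stop. The 12-month gap is a stated design choice. Section 9.7.2 requires each switch on or off Lamzede to be described, with reasons and outcomes. Section 7.2 intends natural-history data to be collected whatever treatment patients receive. Section 9.7.4 does not say that NL-FAS is the comparator for the propensity-score analysis. Restricting the set would also shrink a pool already expected to be limited. What survives is a presentation point: never-treated and post-Lamzede time should be distinguishable in the tables.

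Finally, detailed methods are left to a SAP that is not shown. That does not settle the matter, because the protocol itself fixes the population for these objectives.

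**Conclusion.** The contradiction is literal and should be corrected. As written, none of the on-Lamzede person-time enters the analysis assigned to the potential-risk objective. This follows from the definition of NL-SAF; it does not measure information lost from the final report, since that person-time belongs to L-SAF and would probably be reported under the primary objective. The expectation rests on reading sections 9.7.5 and 9.7.1 and the abstract together, as 9.7.5 names no set.

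The restriction of population characterisation to off-Lamzede time is a second, lesser mismatch of the same kind. How much post-Lamzede time would enter NL-FAS cannot be judged from the protocol. No estimate, sample size or data collection depends on the outcome. This is a wording error in a clause that governs a regulatory safety objective, and it is cheap to put right.

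**What to change.** Amend the last paragraph of section 9.7.1, and carry the change into the SAP:

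- **Safety variables of the secondary objectives.** Analyse potential risks, vital signs, laboratory tests, physical examination and ECG in L-SAF, with event rates per person-years at risk. Show NL-SAF alongside as descriptive background.
- **Population characterisation.** Use all enrolled patients. A one-line definition of that set is needed.
- **Natural history.** Keep this part alone on NL-FAS and NL-SAF, and tabulate never-treated and post-Lamzede person-time separately.
- **Section 9.7.5.** Name the analysis set, so that it agrees with 9.7.1.

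The cost is a few lines of text and a few extra descriptive tables. No new data or assessments are needed, and the precision table in section 9.5 stands. Splitting the untreated time will leave small cells in a pool already expected to be limited, which is acceptable for descriptive tables.

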Lamzede is indicated in patients with alpha-mannosidosis. The marketing authorisation in the EU was granted for Lamzede with European Commission implementing decision of 23rd March 2018. Lamzede is the only authorised treatment for alpha-mannosidosis in the European Union (EU). Prior to its approval, treatment focused on the relief of symptoms, and prevention of complications and impairments, with treatments and procedures designed individually based on symptoms and age. Bone marrow transplantation has been used as a therapeutic strategy for alpha-mannosidosis, but comes with a risk of mortality and morbidity. Palliative treatments include physiotherapy, respiratory physiotherapy or antibiotic treatment for recurrent infections. Prevention of the disease is restricted to prenatal diagnosis and carrier identification.

7.2 Rationale

The Registry is being conducted as an EU Risk Management Plan (EU-RMP) Additional Pharmacovigilance Activities. Lamzede received Orphan Drug Designation in both the EU and the United States, and the marketing authorisation approval in the EU is sought under exceptional circumstances. In connection to Lamzede marketing authorization and its Risk Management Plan, the Alpha-mannosidosis registry is requested to obtain long term data on effectiveness and safety of treatment with Lamzede; furthermore, the Registry will expand the current understanding of alpha-mannosidosis by collecting natural history data, disease modifiers and confounder factors in alpha-mannosidosis patients despite the therapeutic treatment they are receiving.

This study will be conducted in compliance with the Declaration of Helsinki (1964 and amendments), current International Council for Harmonisation (ICH) E6 Good Clinical Practice (GCP) as far as applicable, in accordance with the obligation in the framework of a marketing authorisation granted

Clinical Protocol Number: CLI-LMZYMAA1-12	
Clinical Protocol Version Number: 8.0	Date: 01 February 2019

under exceptional circumstances (category 2 of studies in Good pharmacovigilance practices [GVP] Module V) and all other applicable laws and regulations.

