9.5 Study Size

All patients with alpha-mannosidosis who is willing to participate will be included in the Registry. The size of the registry study is not based on the power to demonstrate a formal statistical hypothesis. However, some scenarios are presented in the table below, considering different proportions of GTR in naïve patients able to perform the functional tests after 3 years of treatment. The proportion of responders, the corresponding expected 95% confidence interval and the confidence width are shown below, assuming at least 70 treated patients will be enrolled.

In this case, it is expected that an exact (Clopper-Pearson) two-sided 95% confidence interval (CI) might be provided with a width ranging from 0.239 (worst case) to 0.199 (best case) assuming GTR of 0.60 or more. Of note, in all scenarios the lower limit of 95% CI is always greater than 45% which is considered a clinical relevant result.

Expected Proportion	95% CI Lower Limit	95% CI Upper Limit	95% CI Actual width
0.60	0.476	0.715	0.239
0.65	0.527	0.760	0.234
0.70	0.579	0.804	0.225
0.75	0.632	0.846	0.214
0.80	0.687	0.886	0.199

Clinical Protocol Number: CLI-LMZYMAA1-12

9.6 Data Management

An eCRF will be filled-in by the investigator and/or his/her representative designee.

Front-end edit checks will run at the time of data collection and back-end edit checks will be used by the Data Manager to check for discrepancies and to ensure consistency and completeness of the data. Questionnaires will be collected on paper and data will be entered in the database by the allocated Contract Research Organisation (CRO).

Medical history, AEs and concomitant procedures will be coded using the Medical Dictionary for Regulatory Activities (MedDRA) dictionary; medications will be coded using the World Health Organization Drug dictionary and Anatomical Therapeutic Chemical classification.

The dictionary version to be use will be the most current version at the time the data collection starts. Considering the long duration of the study, the versions could be updated during the trial by re-coding all terms already entered in database according to the new dictionary version. Re-coded terms will be reviewed by Chiesi for approval.

The detailed process and the coding tools will be specified in the Data Management Plan once the CRO will be selected.

External data (i.e. laboratory data) will be processed centrally^a and results will be sent electronically to the designated CRO.

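### Section 9.7.1 ties the objective of characterising the whole alpha-mannosidosis population to off-Lamzede patient-time only, and defines no all-enrolled set

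*Protocol*

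**What the plan says.** Section 8 states the secondary objective as "To characterize the alpha-mannosidosis population, including clinical manifestation, progression and natural history", with no limit by treatment. It then lists the measures to be used: oligosaccharides, endurance, FVC, hearing, infections, psychotic events, immunoglobulins, quality of life and behaviour. A further secondary item is the incidence of acute renal failure and loss of consciousness, described as potential risks under Lamzede.

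Section 7.2 gives the purpose as collecting natural history data, "disease modifiers and confounder factors in alpha-mannosidosis patients despite the therapeutic treatment they are receiving". Section 9.1 enrols patients whatever treatment they have had or are having. It also warns that the "pool of patients not receiving Lamzede will be limited in number and characterized by distinct clinical features and/ or a short follow-up duration".

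Section 9.7.1 defines four sets: L-SAF, L-FAS, NL-SAF and NL-FAS. The two No-Lamzede sets are defined by patient-time. NL-FAS "will include patients only for the time when they are not (and have not within the 12 months) been taking Lamzede", and NL-SAF is the same with a one-month gap. The primary objective goes to the two Lamzede sets. All secondary objectives go to the two No-Lamzede sets: NL-SAF serves the safety variables, and the remaining analysis rests "on the No-Lamzede Effectiveness analysis set (NL-FAS) for effectiveness and other variables". Section 9.7.3 lists demographics, disease history, genotype and residual enzyme activity, but names no analysis set.

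**The concern.** The objective is about the disease population, but the set assigned to it holds only time off Lamzede. Section 9.1 uses the small and distinctive nature of the no-Lamzede pool to rule out a formal control group. The same property makes that pool a poor stand-in for the whole population. A description of manifestations, genotype or age at onset drawn from it reflects who was not treated, or not yet treated, as well as the disease itself. Larger numbers of the same kind would not remove that selection.

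The rule also misfires on the safety item. The incidence of a potential risk of Lamzede cannot be estimated from time that excludes Lamzede. This suggests that the sentence was written with untreated natural history in mind and then applied to every secondary objective.

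At stake is whether the analysis labelled as answering the secondary objective describes the population it names. The primary effectiveness and safety analyses are not affected.

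**Working it through.** **1. Objective against assigned set.**

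| Item | Scope stated | Set assigned in 9.7.1 | Fit |
|---|---|---|---|
| Characterise the population: manifestations and status (section 8) | All patients, any treatment (7.2, 8, 9.1) | NL-SAF / NL-FAS | Too narrow |
| Progression and natural history (section 8) | No restriction stated | NL-FAS | Reasonable for the untreated course |
| Acute renal failure, loss of consciousness (section 8) | Potential risks under Lamzede | NL-SAF | Excludes the exposure in question |

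No sentence in 9.7.1 assigns a secondary objective to all enrolled patients or to the Lamzede sets.

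**2. Who contributes to NL-FAS.**
- Never treated: all their time.
- Starting Lamzede during the registry: time before the start.
- Stopping Lamzede: time from 12 months after stopping.
- On Lamzede without interruption from before entry: no in-registry time.

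**3. The plan's own figure.** The only size calculation is in section 9.5, for the response rate, "assuming at least 70 treated patients will be enrolled". It uses the Clopper-Pearson interval, with lower limit = Beta quantile(0.025; x, n − x + 1) and upper limit = Beta quantile(0.975; x + 1, n − x). With n = 70 and x = 70p (not an integer at p = 0.65 and 0.75):

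| p | Computed limits | Width | Width in 9.5 |
|---|---|---|---|
| 0.60 | 0.476, 0.715 | 0.239 | 0.239 |
| 0.65 | 0.527, 0.760 | 0.234 | 0.234 |
| 0.70 | 0.579, 0.804 | 0.225 | 0.225 |
| 0.75 | 0.632, 0.846 | 0.214 | 0.214 |
| 0.80 | 0.687, 0.886 | 0.199 | 0.199 |

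The table reproduces. It concerns treated patients only. Its use here is that it gives 70 as the planned minimum of treated patients.

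**4. Illustration of size.** The number of never-treated patients, N, is an assumption, because the documents give none. If the 70 treated patients contribute no untreated time, the share of patients outside the assigned set is 70/(70 + N). Precision is shown as the exact 95% interval width for a characteristic present in half the patients.

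| N assumed | Share outside | Width, N only | Width, all 70 + N |
|---|---|---|---|
| 10 | 70/80 = 87.5% | 0.63 | 0.23 |
| 20 | 70/90 = 78% | 0.46 | 0.22 |
| 30 | 70/100 = 70% | 0.37 | 0.20 |

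For 70 treated and a given N, the share is a maximum: every starter or stopper with untreated time lowers it. The widths show sampling error only and do not include selection.

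**The case against.** Four counter-arguments carry weight.

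- **Treated patients are described elsewhere.** L-FAS is assigned to effectiveness and other variables. By sections 9.7.4 and 9.7.6 these include infections, immunoglobulins, psychotic events, endurance and audiometry. Section 9.7.3 covers genotype, time to diagnosis and history without restricting the set, and it lists Lamzede among the medications, so it evidently expects treated patients. Section 9.7.2 describes every switcher before and after. A reader might infer that most of the registry vanishes from the description of the disease. The documents do not support that: what is missing is treated time in the analysis assigned to this objective.
- **The sets count time, not people.** Starters and stoppers contribute. A reader might also infer that the roughly 30 patients from earlier trials give no untreated time. Section 9.2.1 does not say that they are all on Lamzede at entry or will stay on it. Retrospective data are allowed, and the NL-FAS wording does not clearly bar values from before Lamzede.
- **Untreated time is right for natural history.** Progression on enzyme replacement mixes disease with drug effect. This stands, and NL-FAS should be kept for that part. The objective is wider, however.
- **Details belong to the statistical analysis plan.** This would answer silence about a set. Here the protocol names the set, and the one it names does not match the objective.

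On the safety item, a reader might infer that the potential risks are never tabulated on Lamzede. Section 9.7.5 lists them among the general safety variables, so they may well be reported in L-SAF. It is the stated assignment that cannot answer the objective.

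**Conclusion.** The mismatch holds and rests on the text alone. Section 9.7.1 assigns off-Lamzede time to an objective that sections 7.2, 8 and 9.1 set for patients regardless of treatment, and it offers no all-enrolled set. The literal assignment of the Lamzede potential risks to NL-SAF confirms that the sentence is drawn too broadly.

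The practical size cannot be fixed from the documents. The 70% to 88% range assumes 70 treated and 10 to 30 never-treated patients, with no untreated time from anyone treated, and should be quoted only as an illustration. That treated patients form the majority is itself an inference from the planned minimum of 70 and the expectation of a limited no-Lamzede pool. It would hold as long as fewer than 70 patients contribute only untreated time.

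This should be corrected. It affects the secondary objectives and leaves the primary ones intact.

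**What to change.** In section 9.7.1:

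- Add an All-Enrolled set and base the characterisation objective on it for manifestations, disease history, genotype, diagnosis and baseline status. Show results overall and by treatment status. Use values from before the first Lamzede dose where available, and flag those that are retrospective.
- Keep NL-FAS for untreated progression and natural history.
- Base the rates of acute renal failure and loss of consciousness on L-SAF, with NL-SAF as descriptive context.

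In section 9.7.3, name the All-Enrolled set for the baseline and disease-history tables.

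The cost is a wording change and a few more tables from data the registry already plans to collect. The drawback is that some pre-treatment values will be retrospective and, as section 9.9 acknowledges, of variable availability and quality.
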